Study Description:	Patients with a diagnosis of COVID-19 with critical disease manifestations will be randomly assigned to receive duvelisib or placebo
Objectives:	
Primary Objective: To evaluate the efficacy of duvelisib for the treatment of COVID-19 disease manifestations.
 
Secondary Objectives: To evaluate the safety and tolerability of duvelisib for the treatment of COVID-19 disease manifestations.

Endpoints:	
Primary Endpoint:
 
 • 28 day overall survival 
Secondary Endpoints:
 
 • Hospital and ICU length of stay • Duration of ventilator • Duration of vasopressors • Duration on renal replacement therapy • Viral kinetics • Adverse Events
Study Population:	Twenty-eight patients (approximately 14 per arm) over the age of 18 with a diagnosis of COVID-19 with advanced disease manifestations including one or more of the following: extensive lung involvement, respiratory failure, shock, or cardiac dysfunction.
Phase:	Pilot Phase 2
Description of Sites/Facilities Enrolling:	This is a multi-center study open at Washington University School of Medicine and Missouri Baptist Medical Center.
Description of Study Intervention:	Patients will receive either duvelisib 25mg or placebo for 10 days. Both participants and researchers will be blinded.
Study Duration:	18 months
Participant Duration:	6 months

Table of Contents

PROTOCOL SUMMARY	4
1.0 BACKGROUND AND RATIONALE	7
1.1 COVID-19 and Cytokine Release Syndrome	7
1.2 Lessons and Preclinical Data from CART-related CRS	7
1.3 Gene edited CART model for the Mitigation of CRS	8
1.4 PI3K Inhibition Potently Mitigates CRS in Pre-clinical CART Model.....	9
1.5 PI3K Inhibition to Mitigate Pathogenesis of Advanced COVID-19	10
2.0 OBJECTIVES	11
2.1 Primary Objective	11
2.2 Secondary Objectives.....	11
2.3 Objectives and Endpoints Table	11
3.0 PATIENT SELECTION	12
3.1 Inclusion Criteria	12
3.2 Exclusion Criteria	13
3.3 Inclusion of Women and Minorities	13
4.0 REGISTRATION PROCEDURES	13
4.1 Confirmation of Patient Eligibility	13
4.2 Screen Failures.....	13
5.0 STUDY TREATMENT	14
5.1 Overview.....	14
5.2 Dose Modifications.....	14
5.3 Supportive Care	15
5.4 Viral Load Monitoring.....	17
5.5 Worsening COVID-19 Symptomology	17
5.6 Duration of Therapy.....	17
5.7 Duration of Follow-up	18
5.8 Lost to Follow-Up.....	18
6.0 PHARMACEUTICAL INFORMATION.....	18
6.1 Duvelisib.....	18
7.0 SCHEDULE OF ASSESSMENTS.....	20
8.0 CORRELATIVE STUDIES	22

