2.3 Objectives and Endpoints Table

Objectives	Endpoints	Justification for Endpoints
Primary		
To evaluate the efficacy of duvelisib for the treatment of COVID-19 disease manifestations.	Primary: 28 day overall survival	The expected survival of these patients with advanced COVID-19 symptoms is poor and studies are currently needed.
	Secondary: Hospital and ICU length of stay and duration of ventilator, vasopressors, and renal replacement therapy	In addition to improving survival, duvelisib may reduce the need for these interventions.
Secondary		
To evaluate the safety and tolerability of duvelisib for the treatment of COVID-19 disease manifestations.	Viral kinetics	Duvelisib and similar treatments which modulate cytokine signaling have the potential to reduce immune function which could result in increasing viral loads.
	Adverse events	Adverse events are common with duvelisib for its indicated purpose. It is unclear if similar adverse events are observed in this population.

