3.0 PATIENT SELECTION

3.1 Inclusion Criteria

1. A diagnosis of advanced COVID-19 as defined both of the following:
 - a. as a positive test for SARS-CoV-2 RNA detected by RT-PCR collected from the upper respiratory tract (e.g. nasopharyngeal, nasal, oropharyngeal swab, or saliva) and, if possible, the lower respiratory tract (sputum, tracheal aspirate, or bronchoalveolar lavage), analyzed by a CLIA certified lab with an FDA approved assay. [11]
 - b. Critical disease manifested by any of the following:
 - i. Chest imaging with $\geq 50\%$ lung involvement
 - ii. Respiratory failure requiring invasive mechanical ventilation, non-invasive mechanical ventilation (eg. BiPAP, OptiFlow), supplementary oxygen with ≥ 6 LPM, or extracorporeal membrane oxygenation (ECMO)
 - iii. Shock – defined as mean arterial pressure ≤ 65 mmHg unresponsive to 25ml/kg isotonic intravenous fluid resuscitation and/or requiring vasopressor support (See Appendix A)
 - iv. Cardiac dysfunction defined by:
 1. New global systolic dysfunction with ejection fraction $\leq 40\%$
 2. Takotsubo cardiomyopathy
2. Patients who have received prior investigational or off-label agents for COVID-19 does not exclude eligibility.
3. At least 18 years of age at the time of study registration
4. Adequate hematologic function defined as absolute neutrophil count $\geq 1000/\text{mm}^3$ and platelet count $\geq 50,000/\text{mm}^3$ without growth factor or transfusion support for 7 days prior to screening.
5. Creatinine-clearance ≥ 15 mL/minute or receiving renal replacement therapy (See Appendix B)
6. Aminotransferase (AST/ALT) levels $<3x$ the upper limit of normal
7. Able to understand and willing to sign an IRB approved written informed consent document (or that of legally authorized representative, if applicable)
8. Women of childbearing potential (defined as women with regular menses, women with amenorrhea, women with irregular cycles, women using a contraceptive method that precludes withdrawal bleeding, or women who have had a tubal ligation) are required to have a negative pregnancy test and use two forms of acceptable contraception, including one barrier method, during participation in the study treatment period.

9. Male patients if engaging in sex with a women of childbearing potential are required to use two forms of acceptable contraception, including one barrier method, during participation in the study and throughout the evaluation period.

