12.1 Determination of Sample Size

The primary endpoint is 28 day overall survival (OS). While outcomes data are still developing, observational studies in other areas demonstrate 28-day OS to be poor but highly variable, from approximately 10-40%. [12–14] The variability in outcomes makes a priori sample size calculations difficult, but as this pilot study is designed to generate hypotheses rather than show superiority, sample size considerations were based largely on feasibility and detecting a clinically meaningful effect rather than statistical significance. For duvelisib to have clinically meaningful efficacy, we estimate that 28-day OS is >60% in this patient population. Based on this assumption, a sample size of 28, 14 in each arm, would allow us to detect an improvement in 28-day OS from approximately 20% to 60%, with >80% power at a one-sided type I error of <0.20. If 28 day survival in the placebo cohort is considerably higher, for example 40%, we would only have approximately 40% power in detecting a statistical-significant difference. In either event, additional confirmatory studies that are adequately powered would be needed to more accurately assess the efficacy of duvelisib for the treatment of COVID-19.

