12.2 Statistical Analysis Plan

The primary endpoint is 28 day overall survival (OS) and will be treated as a binary outcome for the purposes of the primary analysis and will be described using descriptive statistics with the corresponding 95% confidence intervals. This will be an intent-to-treat analysis, and all patients randomized will be included in the analysis. The assumption is that all patients will be followed for at least 28 days. Patients who are lost to follow-up for any reason prior to this point will be included in the analysis and considered treatment failures and treated the same as a death. The 28 day OS of each cohort, duvelisib versus placebo, will be compared using Fisher's exact test of independence.

In addition to the primary analysis, OS will be treated as a time-to-event variable and will be described using Kaplan-Meier product limit estimators of event time curves and, if reached, medians with 95% confidence intervals. Cox proportional hazards models may be used to adjust for potential confounding effects. These analyses are considered exploratory, and we acknowledge that the proposed sample size will have low power for such adjustment.

The analyses of secondary end points are all exploratory in nature. Secondary endpoints of efficacy include: hospital and ICU length of stay and duration of ventilator (for those on a ventilator at the time of randomization), vasopressors, and renal replacement therapy. Kaplan-Meier product limit estimators of event time curves and, if reached, medians with 95% confidence intervals, and compared between cohorts using the Log-Rank test. For these analyses, patients will be censored at Day 28 or at death, whichever is earlier. Secondary end points of toxicity are viral kinetics and adverse events. The rate of viral load elevation and other adverse events of interested will be summarized using descriptive statistics and compared using Fisher's Exact tests.

Demographic and clinical characteristics of the sample and of each cohort will be summarized using descriptive statistics. For continuous variables, the number of patients, mean, standard deviation, median, minimum, maximum, and quartiles will be provided. For categorical variables, the number and percent of patients in each demographic/characteristic category will be summarized with 95% confidence intervals.

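### Section 12.2 censors the length-of-stay and support-duration analyses at death, so the Kaplan-Meier curves overstate how many patients leave hospital or come off support; a count of new ventilation would be a cheap addition

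*Combined protocol and SAP*

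**What the plan says.** Section 12.2 lists the secondary efficacy endpoints as hospital and ICU stay and "duration of ventilator (for those on a ventilator at the time of randomization), vasopressors, and renal replacement therapy". They are to be described by Kaplan-Meier curves and, where reached, medians with 95% confidence intervals, and compared by log-rank. The censoring rule is "For these analyses, patients will be censored at Day 28 or at death, whichever is earlier". Section 12.2 calls all secondary analyses exploratory.

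The Protocol Summary gives the support endpoints without a population limit: "Duration of ventilator • Duration of vasopressors • Duration on renal replacement therapy". So does the table in section 2.3: "Hospital and ICU length of stay and duration of ventilator, vasopressors, and renal replacement therapy". The justification there is "In addition to improving survival, duvelisib may reduce the need for these interventions".

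Section 3.1 requires "Critical disease manifested by any of the following". The list includes imaging findings, supplementary oxygen, shock and cardiac dysfunction, so a patient can enter without being ventilated.

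For safety, section 12.2 says "The rate of viral load elevation and other adverse events of interested will be summarized using descriptive statistics", with Fisher's exact tests between arms. New ventilation is not named among those events.

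**The concern.** The main issue is the handling of death. Censoring assumes that the censored patient could still have the event later, at the same rate as those who remain under observation. That is reasonable for a patient alive and still ventilated at Day 28. It fails for a patient who has died on the ventilator, for whom coming off is no longer possible. Kaplan-Meier passes that patient's probability to the survivors, and the curve then answers a hypothetical question: how many would come off if nobody died. In a population where section 12.1 plans for 28-day survival of about 20% on placebo and 60% on duvelisib, that is far from what happens to patients. Because mortality may differ between arms, the overstatement may differ too, and the curves could suggest a contrast that the proportions do not show, or alter a real one.

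The second issue is smaller. Section 2.3 speaks of reducing the need for these interventions. Shorter use is one form of that, and never starting is another. Patients not ventilated at entry contribute nothing to the ventilator analysis, and no listed endpoint counts how many of them are later ventilated.

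**Working it through.** **The plan's own figures.** The documents give no figure for these secondary endpoints. The power statements in section 12.1 concern the primary endpoint. They reproduce with an exact one-sided Fisher test at 0.20 and 14 per arm: 82.7% for 20% versus 60% and 40.1% for 40% versus 60%. Nothing below changes them.

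**Effect of censoring at death.** Let d be the proportion who die on support by Day 28 and o the proportion who truly come off by then. Both are assumed, because the documents give neither for this subset. With constant hazards over 28 days:

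- total cumulative hazard: H = -ln(1 - d - o)
- share of H due to coming off: h = H × o/(o + d)
- what the censored analysis shows: 1 - KM = 1 - exp(-h)

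Holding the true proportion at o = 15%:

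| d | H | h | 1 - KM | True |
|---|---|---|---|---|
| 80% | -ln(0.05) = 2.996 | 2.996 × 0.15/0.95 = 0.473 | 38% | 15% |
| 70% | -ln(0.15) = 1.897 | 1.897 × 0.15/0.85 = 0.335 | 28% | 15% |
| 60% | -ln(0.25) = 1.386 | 1.386 × 0.15/0.75 = 0.277 | 24% | 15% |
| 40% | -ln(0.45) = 0.799 | 0.799 × 0.15/0.55 = 0.218 | 20% | 15% |

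The estimate is too high in every row, and more so as deaths rise.

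**Medians.** Take d = 40% and o = 50%. Then H = -ln(0.10) = 2.303, h = 2.303 × 0.50/0.90 = 1.279, and 1 - KM is 72%. The true proportion reaches one half only at Day 28. The Kaplan-Meier median falls at 28 × 0.693/1.279, about Day 15.

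**Contrast between arms.** This uses d = 80% on placebo and d = 40% on duvelisib purely as an illustration:

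| True, placebo vs duvelisib | Shown by 1 - KM | True difference | Shown difference |
|---|---|---|---|
| 15% vs 50% | 37.7% vs 72.2% | 35 points | 34.5 points |
| 10% vs 30% | 22.6% vs 40.3% | 20 points | 17.7 points |
| 15% vs 15% | 37.7% vs 19.6% | 0 points | -18.1 points |

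Each arm's level is overstated in all three cases. The difference may barely move or may move a good deal, depending on the inputs.

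**Coverage of the ventilator analysis.** The documents do not give the share not ventilated at entry. At an assumed 30% to 70%, 28 × 0.30 = 8.4 to 28 × 0.70 = 19.6 patients fall outside it, or 4 to 10 per arm.

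**Precision of a count of new starts.** With 0 starts among 4, 7 or 10 patients, the exact 95% upper limit is 1 - 0.025^(1/n) = 60%, 41% or 31%. With 4 of 7, the exact interval is 18% to 90%. Exact one-sided Fisher power at 0.20 for 40% versus 20% is 8%, 26% and 41% with 4, 7 and 10 per arm. A count is informative as description; a test is not.

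**The case against.** **The baseline restriction is sound.** Time to coming off a ventilator needs patients who are on one, and fixing that set at randomization avoids selecting on a later event. A reader might infer that section 12.2 contradicts section 2.3 and the Protocol Summary. It does not: it makes a short label operational. This stands. What remains is that no companion measure covers the other patients. The parenthesis also attaches only to the ventilator, so the documents do not show that vasopressors or renal replacement therapy are limited in the same way.

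**The log-rank test is not wrong.** With deaths censored, it validly compares the rate of coming off among patients still alive and on support. In the 15% versus 15% example, 5% of placebo patients and 45% of duvelisib patients are alive and still on support at Day 28, and the cumulative cause-specific hazards are 0.47 and 0.22. Duvelisib patients there do come off more slowly per day at risk. This stands too. The fault lies in reading the curves and medians as proportions and times for all patients in the analysis.

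**The mortality inputs are assumptions.** A reader might infer that section 12.1 fixes deaths on support at 80% and 40%, and so predicts a false advantage for placebo. Its figures are planning values for overall survival in all randomized patients, and it calls reported survival highly variable, at about 10% to 40%. Deaths on support in a baseline subset are given nowhere. The direction of the overstatement is certain wherever deaths precede the event; its size is not.

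**New ventilation is not invisible.** A reader might infer that it goes unrecorded. Adverse events are tracked through Day 29 (section 10.0), events exempt from expedited reporting still enter the database (section 10.3), and SOFA and APACHE II are scheduled at Day -1 and Day 10 (section 7.0). These are indirect routes: section 12.2 names neither new ventilation nor the scores for analysis.

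**The analyses are exploratory in a 28-patient pilot.** True, and it limits the weight of the point. It does not make a misleading estimate useful for generating hypotheses.

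**Conclusion.** The concern holds for censoring at death. As planned, the Kaplan-Meier curves for both lengths of stay and all three support durations overstate the proportion discharged or off support whenever patients die first, and they shorten the medians. Under constant hazards with 15% truly coming off, the overstatement runs from about 5 points at 40% mortality on support to about 23 points at 80%. All of those inputs are assumed. The documents do not support a claim that the comparison between arms will be reversed, that the log-rank test is invalid, or that the primary 28-day survival analysis is affected.

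The missing count of new ventilation is a lesser point. It concerns one of two readings of reduced need in section 2.3, and adding it is a cheap improvement, not the repair of an error.

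**What to change.** In section 12.2, replace the censoring sentence with:

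> For hospital and ICU length of stay and for time to coming off ventilator, vasopressors and renal replacement therapy, death before the event is a competing event. Cumulative incidence to Day 28 will be reported by arm with 95% confidence intervals and compared by Gray's test. Patients alive and event-free at Day 28 are censored then. Any log-rank test retained will be labelled a comparison of cause-specific hazards.

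Keep the baseline limit for ventilator duration, and add:

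> Among randomized patients not on a ventilator at randomization, the number and proportion starting one by Day 28 will be reported by arm with exact 95% confidence intervals, with deaths without ventilation shown alongside, using the same definition of ventilator as the duration endpoint. The same count will be reported for vasopressors and renal replacement therapy.

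No test of new starts is proposed. For the definition to work, section 12.2 should say whether ventilator includes the non-invasive support listed in section 3.1. It should also say which patients enter the vasopressor and renal replacement duration analyses.

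The cost is plan wording and possibly a form field for support status at randomization and start date. Section 9.0 lists form names only, so the documents do not show whether these are already collected. The downside is wide intervals for both the counts and the cumulative incidence curves in subsets this small.

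### Hospital stay and organ-support durations are analysed with deaths censored, so the Kaplan-Meier curves and medians do not describe leaving hospital or coming off support alive

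*Combined protocol and SAP*

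**What the plan says.** Section 12.2 lists the secondary efficacy endpoints as hospital and ICU length of stay and the time on ventilator, vasopressors and renal replacement therapy. Ventilator time is restricted to patients ventilated at randomization. The method is "Kaplan-Meier product limit estimators of event time curves and, if reached, medians with 95% confidence intervals, and compared between cohorts using the Log-Rank test". Deaths are handled in one sentence: "For these analyses, patients will be censored at Day 28 or at death, whichever is earlier". The event is not named, but under this rule it can only be discharge, or end of support, while alive. The plan has no cumulative incidence function, competing-risk test, support-free days or other rule for deaths.

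Section 2.3 gives the purpose of these endpoints: "In addition to improving survival, duvelisib may reduce the need for these interventions". Section 12.1 describes "28-day OS to be poor but highly variable, from approximately 10-40" percent, and says that the sample size "would allow us to detect an improvement in 28-day OS from approximately 20% to 60" percent. Section 12.2 also states: "The analyses of secondary end points are all exploratory in nature".

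**The concern.** Kaplan-Meier censoring assumes that a censored patient has the same future chance of the event as those still under observation. That is reasonable for a patient still in hospital at Day 28. It is false for a patient who has died. The estimator hands that patient's chance of discharge to those who remain, so the estimated proportion discharged is too high and the median is not the length of stay of this population.

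On the plan's own figures this is not a rare event. Survival of 20% and 60% with 14 per arm means about 0.80 × 14 = 11 deaths on placebo and 0.40 × 14 = 6 on duvelisib, so up to that many patients censored by death. The distortion grows with mortality, so it differs between arms exactly when the drug changes survival. In a trial meant to generate hypotheses, the risk is a secondary signal on duration that hides a benefit or points the wrong way.

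**Working it through.** **Inputs.** From the documents: 14 per arm, a 28-day horizon, survival of 20% and 60%, and 40% as the alternative placebo rate (Sections 12.0 to 12.2). The plan gives no figure for the duration endpoints. Its power figures for the primary endpoint do reproduce: Fisher's exact test, one-sided 0.20, 14 per arm, gives 82.7% (stated as above 80%) and 40.1% (stated as about 40%). Discharge rates are not in the documents, so every discharge or frailty hazard below is an assumption. Deaths after discharge are ignored.

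**1. A 14-patient example.** Eleven patients die (days 3, 4, 5, 6, 7, 8, 9, 11, 12, 14, 16), two are discharged (days 13 and 20) and one is in hospital at Day 28. With deaths censored, 5 are at risk on day 13 and 2 on day 20. Kaplan-Meier is (4/5) × (1/2) = 0.40, so one minus Kaplan-Meier is 60%, with a median of 20 days. In fact 2/14 = 14.3% were discharged. Keeping the deaths in the risk set to Day 28 without an event gives exactly 14.3%.

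**2. Equal discharge hazard in both arms.** Let r be the daily hazard of discharge and d that of death, both constant.

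- Discharged alive by Day 28: r/(r+d) × [1 − exp(−28(r+d))]
- One minus Kaplan-Meier at Day 28: 1 − exp(−28r)
- Kaplan-Meier median: ln 2 / r

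The hazard d is solved so that 28-day mortality matches the plan. With r = 0.03:

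- 20% survival, d = 0.1277: 0.03/0.1577 × [1 − exp(−4.416)] = 18.8%
- 40% survival, d = 0.0574: 0.03/0.0874 × [1 − exp(−2.447)] = 31.4%
- 60% survival, d = 0.0293: 0.03/0.0593 × [1 − exp(−1.660)] = 41.0%
- One minus Kaplan-Meier, all three: 1 − exp(−0.84) = 56.8%
- Median, all three: 0.693/0.03 = 23.1 days

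| Assumed r per day | Discharged alive, 20% survival | Discharged alive, 60% survival | One minus KM, both |
|---|---|---|---|
| 0.02 | 16.3% | 31.8% | 42.9% |
| 0.03 | 18.8% | 41.0% | 56.8% |
| 0.05 | 19.9% | 51.7% | 75.3% |
| 0.08 | 20.0% | 57.7% | 89.4% |

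**3. A different assumption.** Fix instead the share of 28-day survivors discharged by Day 28 at 75% (range 50 to 90%). At 20% survival, r+d = −ln(1 − 0.80 − 0.15)/28 = 0.1070 and r = 0.1070 × 0.15/0.95 = 0.0169. One minus Kaplan-Meier is then 38%, against a true 15%.

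| Survival | True, 75% (range) | One minus KM, 75% (range) |
|---|---|---|
| 20% | 15% (10 to 18%) | 38% (23 to 51%) |
| 40% | 30% (20 to 36%) | 54% (33 to 70%) |
| 60% | 45% (30 to 54%) | 63% (40 to 80%) |

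**4. Frailer patients die more and leave more slowly.** Assume half the patients are frail, discharge hazards of 0.01 (frail) and 0.06 (robust), a frail death hazard 3 times the robust one, and a drug that acts on death only. The curve then follows the average discharge hazard of those still in hospital, a group that loses its frail members faster where mortality is higher. At 20% against 60% survival, 19.5% and 42.6% are discharged alive, but the Kaplan-Meier medians are 14.7 days (placebo) and 21.5 days (duvelisib). At 40% against 60% survival they are 18.7 and 21.5 days.

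Four settings at 20% against 60%, with 3,000 simulated trials each and 14 per arm:

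| Discharge hazard frail/robust; death hazard ratio | KM median, placebo vs duvelisib (days) | Log-rank towards arm with more deaths | Significant that way (two-sided 5%, assumed) |
|---|---|---|---|
| 0.01/0.06; 3 | 14.7 vs 21.5 | 61.8% | 6.3% |
| 0.01/0.06; 6 | 12.8 vs 20.3 | 68.3% | 9.2% |
| 0.01/0.10; 6 | 7.8 vs 14.4 | 71.0% | 10.7% |
| 0.02/0.06; 3 | 13.7 vs 17.6 | 58.5% | 5.8% |

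Without frailty (0.03 per day in both arms) the log-rank direction splits 51/49, as it should when the discharge hazards are equal.

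**The case against.** The case for leaving the plan alone has several parts.

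- **Exploratory status.** The plan labels these analyses exploratory, says confirmatory trials would be needed, and counts deaths directly in the primary endpoint. This stands and limits the severity. It does not correct a reported median stay.
- **The log-rank is valid.** With deaths censored it compares discharge rates among patients still alive and in hospital, and with equal rates it rightly shows no difference. This stands. But the plan does not label it cause-specific, and the curves and medians have no such defence.
- **Competing-risk summaries also register mortality.** With deaths kept to Day 28 as not discharged, the comparison points to the arm with more survivors in 89 to 94% of the frailty simulations, but also in 89% when discharge hazards are equal. This stands: that figure is no evidence that the alternative measures duration better. The case for it is that it estimates a proportion that exists.
- **The hazards are assumed, and some are high.** At 0.03 per day, 18.8/20 = 94% of placebo survivors and 41.0/60 = 68% of duvelisib survivors are home by Day 28. If only 50 to 75% of survivors are discharged at 20% survival, the placebo Kaplan-Meier median is not reached, and the plan would report none. So the size, and whether a misleading median appears, depend on the discharge rate. The direction of the overstatement does not.
- **Scope.** Simulations with 14 per arm fit hospital stay. Ventilator time, for one, would rest on fewer patients. The argument carries over to the support endpoints, but these percentages do not.

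**Conclusion.** The concern holds. Under the stated censoring rule, one minus Kaplan-Meier overstates the proportion leaving hospital or coming off support alive whenever deaths precede later events. The medians are then not this population's durations.

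At the plan's 20% and 60% survival and assumed discharge hazards of 0.02 to 0.08 per day, the true proportions are 16 to 20% and 32 to 58%. The planned curve shows 43 to 89%, identical in the two arms. Reversed medians need the added assumption that the patients likeliest to die are also the slowest to leave. They are a plausible illustration, not a forecast.

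The flaw is confined to exploratory secondary endpoints. The primary analysis, the sample size and the log-rank test as a cause-specific comparison are sound. It should be corrected because death is expected to be common and the purpose in Section 2.3 is not answered by these curves.

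**What to change.** In Section 12.2, replace the censoring sentence with a rule that treats death as a competing event.

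- Name the event: discharge alive, or coming off the given support alive.
- Report its cumulative incidence to Day 28 by arm with 95% confidence intervals, and compare arms by Gray's test.
- Take any median from that curve, and report it as not reached where the curve stays below 50%.
- As an acceptable alternative, use days alive and free of hospital, ICU or support to Day 28, with death scored 0.
- If the log-rank with deaths censored is kept, call it a cause-specific comparison and show the cumulative incidence curves beside it.

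Both replacements reflect mortality as well as duration, so the text should say that they are read alongside 28-day survival.

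The cost is SAP wording only. The death form and the 28-day survival form are already in the data submission schedule (Section 9.0).
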